6. TREATMENT DESCRIPTION

The standardized multidisciplinary method under study is a weight loss program consisting of different stages. The initial stage (stage 1) is based on a protein diet, a type of ketogenic diet very low in calories. This stage is followed by a physiological adaptation stage (stage 2) in which all food groups are reintroduced progressively, and a maintenance phase (stage 3) with long-term monitoring of the patient's weight to ensure stability of the results obtained. This program contemplates other essential aspects in the management of obese patients, such as dietary education, physical activity and psychological support throughout the treatment.

80% of target weight loss			20% of target weight loss	Long-term maintenance of weight loss
Multidisciplinary team (dietary counselling / physical activity / psychological support)				
Stage 1 Active Stage		Stage 2 Dietary re-education		Stage 3 Maintenance
Phase 1	Phase 2	Phase 3	Gradual re-introduction of different foods	
VLCK diet ¹ (600-800 kcal/day)		LC diet ² (800-1500 kcal/day)		Maintenance diet (1500-2250 kcal/day)

The stage 1 protein diet is established through the intake of high biological value proteins and low-glycaemic vegetables, supplemented with micronutrients (potassium, sodium, calcium, magnesium, vitamins and trace elements) to avoid deficiencies. This stage consists of 3 phases (Phase 1, Phase 2a and Phase 2b), in which a protein preparation and then a second protein preparation are replaced progressively by protein-rich natural foods (meat/fish/eggs). During this period of ketogenic diet, the patient will be visited by the doctor every fortnight.

The ketogenic stage 1 of the method will be maintained for 2 months for those patients with an initial BMI of 30 to 35 kg/m² and for 3 months for those patients with initial BMI > 35 kg/m².

Stage 2 begins after the initial loss of most of the weight to be lost (ideally 80%), with the progressive introduction of different foods, while reducing protein preparations at the same time. In this way the weight loss indicated by the doctor is finally reached and the food balance is also achieved. This stage will be maintained for a period of 4 months in patients with an initial BMI of 30 to 35 kg/m² and for 6 months for those patients with initial BMI > 35 kg/m².

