10.2. Analysis of objectives

The primary objective analysis will include:

- Costs of weight loss treatment estimated from the cost of: protein products and dietary supplements + number of control visits + number of laboratory tests performed
- Healthcare expenditure estimated as the sum of the following costs: pharmacological treatment of associated comorbidities, incidence of

complications (visits to his/her primary care physician, a specialist or emergency department for acute complications, treatment of acute complications, number of hospital admission days, antibiotic treatment), consumption of health resources (visits to the general practitioner, visits to specialists, laboratory tests)

- Work absenteeism, estimate of the number of work leave days + hours of work absenteeism due to health problems or medical visits.

In order to evaluate if the weight loss treatment is improving the health of patients and reducing health expenditure and absenteeism, the healthcare expenses and work absenteeism estimated from the doctor's records corresponding to the 6 months prior to the initiation of the weight loss treatment will be compared with data recorded at follow-up visits over the 2-year follow-up. Likewise, the doses and number of drugs required by patients for the treatment of their comorbidities before the weight loss and at the control visits during weight loss and up to completing the 2 years of follow-up will be compared.

As secondary objectives, the efficacy of the weight loss treatment will be studied by comparing the anthropometric parameters of the initial visit with those of the follow-up visits (weight, body mass index and waist circumference). Likewise, any improvement in laboratory parameters and blood pressure during the follow-up will be studied. Changes in quality of life scores (SF-12) will also be assessed between the initial visit and the end of each treatment stage.

For all objectives, the comparisons between qualitative variables will be made using the Chi square test or the Fisher exact test, and the comparison between quantitative variables will be performed using the Student's t-test (in the case of 2 groups) or by the one-way ANOVA test (for 3 or more groups). If the conditions for the Student's t-test or the Anova test are not met, the non-parametric Mann-Whitney U test (2 groups) or the Kruskal-Wallis test (for 3 or more groups) will be used.

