Safety and tolerability will be analysed by descriptive statistics of all side effects or adverse reactions reported by patients throughout the study.

For all tests, the significance level will be set at $p < 0.05$.

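### Section 10.2 compares the same patients before and after treatment but names only tests for independent groups, so the p-values are miscalibrated (conservative if within-patient correlation is positive)

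*Combined protocol and SAP*

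**What the plan says.** Sections 4 and 5 describe a single, non-randomised cohort receiving the weight loss method, with no comparison group.

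The comparisons in section 10.2 are all over time in that cohort:

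- **Expenditure and absenteeism:** data from "the 6 months prior to the initiation of the weight loss treatment will be compared with data recorded at follow-up visits" over two years.
- **Drug treatment:** doses and number of drugs before weight loss against those at the control visits.
- **Anthropometry:** "comparing the anthropometric parameters of the initial visit with those of the follow-up visits". Improvement in laboratory values and blood pressure is also studied during follow-up.
- **Quality of life:** "Changes in quality of life scores (SF-12) will also be assessed between the initial visit and the end of each treatment stage".

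One list of tests then covers every objective. For categorical data, "comparisons between qualitative variables will be made using the Chi square test or the Fisher exact test". For continuous data, "the comparison between quantitative variables will be performed using the Student's t-test (in the case of 2 groups) or by the one-way ANOVA test", the latter for three or more groups. If their conditions fail, "the non-parametric Mann-Whitney U test (2 groups) or the Kruskal-Wallis test (for 3 or more groups) will be used".

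Two parts involve no test and are not affected: safety ("Safety and tolerability will be analysed by descriptive statistics of all side effects or adverse reactions") and the cost of the weight loss treatment, which is an estimate.

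**The concern.** Two measurements on one patient are usually correlated, and an independent-groups test ignores this. It computes the standard error of the mean change as if the earlier and later values came from different people. If the correlation is positive, that standard error is too large, the p-value is too large, and a real change can be declared non-significant.

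This reaches every hypothesis test in the study, including the tested parts of the primary objective. A missed reduction in expenditure or absenteeism could be reported as no reduction. Section 5.3 gives no power calculation for the 200 patients, so nothing shows that the loss can be absorbed.

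Dropout adds a second problem. An unpaired comparison of everyone at baseline with those still attending mixes change over time with a change in who is measured. That is partly a missing-data issue, which a paired test in completers would not solve.

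**Working it through.** The plan has no calculated figure to reproduce, so the check has two parts: which tests the text names, and what they do to paired data.

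**Reading the text.** Student's t-test could by itself mean the paired form. Here it is reserved for two groups, its fallback is Mann-Whitney rather than signed-rank, and its extension is one-way ANOVA with Kruskal-Wallis as fallback. That is the independent-samples family. Even if the t-test were read as paired, the other five named tests would still ignore pairing. Section 10.2 describes no comparison between groups of patients for which the list would be right.

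**Inputs.** n = 200 (section 5.3) and alpha = 0.05 (section 10.2), taken as two-sided because sidedness is not stated. Assumed: complete pairs, within-patient correlation r, and a true change d in SD units.

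**Two time points, equal SDs.** The true standard error of the mean change is sqrt(2(1−r)/n). The planned test uses sqrt(2/n) = sqrt(2/200) = 0.1. Hence:

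- SE inflation = 1/sqrt(1−r)
- actual type I error = 2[1 − Φ(1.96/sqrt(1−r))]
- planned power = Φ((d/0.1 − 1.96)/sqrt(1−r))
- paired power = Φ(d/(0.1·sqrt(1−r)) − 1.96)

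Example, r = 0.5 and d = 0.2: planned Φ(0.04/0.707) = 52.3%; paired Φ(2/0.707 − 1.96) = 80.7%.

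| r | SE inflation | Actual type I error | Power at 0.2 SD, planned | Power at 0.2 SD, paired |
|---|---|---|---|---|
| 0.1 | 1.05 | 3.9% | 52% | 56% |
| 0.3 | 1.20 | 1.9% | 51.9% | 66.7% |
| 0.5 | 1.41 | 0.56% | 52.3% | 80.7% |
| 0.7 | 1.83 | 0.035% | 52.9% | 95.5% |

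At r = 0 there is no error. At r = −0.3 the direction reverses and type I error is 8.6%.

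**Larger changes, same assumptions.** At 0.3 SD, planned against paired power is 89% against 95% (r = 0.3), 93% against 99% (r = 0.5) and 97% against 100% (r = 0.7). At 0.4 SD both are at least 99%. With only 100 pairs, 0.4 SD and r = 0.5, it is 89% against 98%.

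**Unequal SDs.** If the follow-up SD is k times the baseline SD, as could happen if raw 6-month and 2-year totals were compared, inflation = sqrt((1+k²)/(1+k²−2rk)).

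| r | Inflation, k = 2 | Inflation, k = 4 | Type I, k = 2 | Type I, k = 4 |
|---|---|---|---|---|
| 0.3 | 1.15 | 1.08 | 2.5% | 3.4% |
| 0.5 | 1.29 | 1.14 | 1.1% | 2.5% |
| 0.7 | 1.51 | 1.22 | 0.3% | 1.7% |

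**The other named tests**, simulated with no true change, n = 200, nominal 5%:

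| Test | 0.3 | 0.5 | 0.7 |
|---|---|---|---|
| Mann-Whitney, 2 visits | 2.2% | 0.65% | 0.08% |
| Chi-square, paired binary, 50% prevalence | 1.9% | 0.54% | 0.04% |
| One-way ANOVA, 7 visits, equal correlation | 0.7% | 0.05% | 0% |
| Kruskal-Wallis, 7 visits, equal correlation | 0.9% | 0.08% | 0% |

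Seven visits are the baseline plus the six control visits in section 7.2. The margin depends on the correlation pattern: in a contrived two-block pattern (0.95 within blocks, 0 between) the ANOVA error was 4.4%.

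**SF-12 at four time points** (initial visit and end of three stages). With assumed changes of 0, 0.16, 0.20 and 0.20 SD and equal correlation of 0.3, 0.5 or 0.7, simulated power is 40%, 35% or 27% for one-way ANOVA, against 62%, 79% or 96% for repeated-measures ANOVA.

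**The case against.** The strongest reply is that the error is safe. It is conservative, it leaves the estimated mean change alone when pairs are complete, and the plan makes no power claim that it would break. Nor do before/after p-values settle a cost-effectiveness question. All of this is true. It limits the harm to missed findings but does not make the tests valid for this design.

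The size is also uncertain. Nothing in the documents implies r of 0.3 or more for costs or absenteeism. At r = 0.1 the type I error is 3.9% with equal SDs and 4.5% with k = 4. For changes of 0.4 SD or more in 200 complete pairs, the power loss almost disappears. This stands: the magnitude is unknown and may be small for some outcomes.

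The SF-12 illustration is the weakest part. Its pattern borrows the 80% that section 6 gives for target weight loss, which says nothing about SF-12. The text can also be read as separate two-point contrasts. The conclusion does not depend on it.

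Finally, since the plan speaks of changes, the authors may have intended within-patient analysis. If so, the test list contradicts the intention and still needs correcting.

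**Conclusion.** The concern holds. The tests named in section 10.2 do not match the design for any tested objective. Followed as written, they give p-values that are too large when within-patient correlation is positive, and too small when it is negative.

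With r between 0.3 and 0.7, equal SDs and 200 complete pairs, the standard error is inflated by 1.20 to 1.83. Power for a 0.2 SD change stays near 52%, when a paired test would give 67% to about 95%. The inflation is smaller with unequal SDs (1.08 to 1.51 for k of 2 or 4) and negligible near r = 0. These figures rest on assumed correlations and effect sizes; the mismatch itself does not.

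This should be corrected before analysis. Otherwise the analyst must either run an unsuitable test or choose another after seeing the data.

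**What to change.** In section 10.2, replace the test list for before/after comparisons:

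- **Continuous outcomes:** paired t-test for a single contrast, or a mixed model for repeated measures across visits using all available data.
- **Ordinal or skewed non-cost outcomes**, such as number of drugs: Wilcoxon signed-rank.
- **Costs and absenteeism:** mean within-patient difference with a patient-level (paired) bootstrap 95% CI.
- **Binary outcomes:** McNemar, or a GEE logistic model across visits.

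Report the mean within-patient change with its 95% CI and state how missing visits are handled. Keep the independent-groups tests only for comparisons between patient subgroups, such as BMI 30-35 against above 35.

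Define visits by stage or by actual time. Section 6 says "The ketogenic stage 1 of the method will be maintained for 2 months for those patients with an initial BMI of 30 to 35", followed by 4 months of stage 2, so stage 2 ends at month 2 + 4 = 6. For BMI above 35 it ends at month 3 + 6 = 9.

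The minimum correction is one paired method per type of variable plus one repeated-measures method; the rest makes better use of the data. The cost is a paragraph of analysis wording, with no extra data or patients. Pairing does not resolve the unequal 6-month and 2-year windows, dropout or the lack of a comparator, which need separate attention.

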3.2. Secondary objectives

- Assess short and long-term weight loss and waist circumference reduction
- Assess the degree of clinical and laboratory improvement of cardiovascular risk factors (HTN, diabetes, dyslipidaemia) associated with weight loss
- Evaluate patient quality of life improvement in relation to weight loss
- Assess the tolerability and safety of the weight loss treatment.

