4. STUDY DESIGN

Prospective, observational, multicenter study based on a registry of patients with obesity and associated comorbidities undergoing a standardized multidisciplinary weight loss method with a 2-year follow-up.

No randomization or administration of drug treatment is intended as a consequence of the patient's participation in the study.

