5.3. Number of patients

Expected number of subjects is 200 patients. Subjects who initiate the multidisciplinary weight loss treatment during the study inclusion period, meet the inclusion and exclusion criteria, and agree to participate and sign the informed consent will be included in the study.

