The last stage of the method begins at this moment, which involves the long-term maintenance of the lost weight, with the supervision and monitoring of specialized dietitians/nutritionists who advise patients in terms of consolidation of their new dietary habits, that is, the establishment of a balanced diet, which is the ultimate goal of the method.

The method must be implemented under strict medical supervision to ensure the efficacy and, above all, the safety of the program. In addition, the program is supported

by dietitians/nutritionists who help control the patient's progress (with continuous on-site and/or telephone follow-up over the 2 years of treatment) and a team of psychological counselling professionals and experts in physical activity.

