7.2. Follow-up period

The expected follow-up period for each patient will be 2 years from the time of inclusion, recording data during the weight loss and maintenance periods. The registry of patient data for this study will be made by the doctor and the dietitians/nutritionists who will regularly see the patient in the face-to-face visits at the Pronokal centre. For this, a specific form will be designed in which information about the variables to be studied will be collected.

Before starting treatment with the standardized multidisciplinary method and its inclusion in the study, the physician will have performed a first patient pre-inclusion visit (day -15) to request complementary tests (laboratory and ECG) and rule out the existence of contraindications to the ketogenic diet part of the weight loss program.

The study will begin with the baseline visit (day 0) in which the inclusion and exclusion criteria will be confirmed, the signing of informed consent will be obtained and the multidisciplinary treatment will be prescribed, followed by 6 control visits: 2 visits during the ketogenic stage (1-month after the start and at the end of ketosis), 2 visits during the physiological adaptation phase (at 4 or 5 months and at the end of stage 2) and 2 follow-up visits during the maintenance up to the 2-year completion. Regardless of the visits established in this protocol, the doctor will make as many visits as he/she deems necessary for good patient control.

On the other hand, dietitians/nutritionists, according to the methodology of the program, will carry out a face-to-face follow-up of the patient, which will be fortnightly during the ketogenic diet, monthly during the physiological adaptation of stage 2 and quarterly or semi-annual during the maintenance stage.

In the **pre-inclusion visit (day -15)**, the physician will perform a first clinical assessment of the patient. He/she will record the sociodemographic data, history of diabetes, comorbidities, pharmacological treatments. He/she will request complete laboratory tests and will perform an electrocardiogram to rule out contraindications and verify the inclusion/exclusion criteria. The said laboratory tests will include:

- Complete blood count and leukocyte formula
- Hydrocarbon metabolism: fasting glycemia, HbA1c, insulinemia
- Lipid profile: total cholesterol, LDL-C, HDL-C, triglycerides
- Transaminases: GOT, GPT, gammaGT

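### If the rule for three or more groups is applied across visits, it tests only whether all visits are equal; no within-patient comparison with month 24 is designated for the long-term claims

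*Combined protocol and SAP*

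**What the plan says.** Section 3.2 makes both time horizons an objective: "Assess short and long-term weight loss and waist circumference reduction". Section 6 describes a final stage "which involves the long-term maintenance of the lost weight". Section 7.2 sets a baseline visit "followed by 6 control visits": two in the ketogenic stage, two in the adaptation stage and two in maintenance up to 2 years.

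Section 10.2 plans to study efficacy by "comparing the anthropometric parameters of the initial visit with those of the follow-up visits". SF-12 change is to be assessed from the initial visit to the end of each stage. Costs and absenteeism in the 6 months before treatment are compared with the follow-up data, and drug doses and counts before treatment with those at the control visits.

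One set of tests then serves every objective. Quantitative variables get Student's t-test for two groups and "the one-way ANOVA test (for 3 or more groups"), with Mann-Whitney and Kruskal-Wallis as fallbacks. Section 10.2 ends with "For all tests, the significance level will be set at" p < 0.05. It names no post-hoc test, planned contrast, key time point or rule for concluding long-term benefit.

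There is no comparison arm. Section 4 states "No randomization or administration of drug treatment is intended as a consequence of the patient's participation in the study", and section 5 defines a single treated population. Section 5.3 gives the size without derivation: "Expected number of subjects is 200 patients".

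**The concern.** The questions are directional and relative to baseline: is the patient better off than before treatment, early on and at 2 years? A one-way ANOVA or Kruskal-Wallis test across visits has a different null hypothesis, that all visits share one mean or distribution. Any difference between any two visits counts against it, including a low point in the diet stage against month 24, or a rise above baseline.

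This matters for this method in particular. It is built to give rapid loss followed by maintenance, so loss followed by regain is an obvious way for it to fail. An overall visit test cannot tell that failure from lasting success. At stake is whether a reported p-value can support the long-term claims for weight, waist, laboratory values or drug use.

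The point is separate from the neglect of pairing. A repeated-measures ANOVA would respect the pairing and still test the same null.

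**Working it through.** The plan has no calculation to reproduce: 200 is an expected number, with no SD, effect size, power or dropout behind it. The check asks how often the overall test is significant when the long-term answer is no change.

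**Inputs from the documents.** n = 200 (5.3); k = 1 + 6 = 7 visits (7.2); level 0.05 (10.2).

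**Assumptions, not in the documents.** Complete, normally distributed data; equal SD at every visit; equal correlation ρ between visits; the last maintenance visit at month 24. The mean profile is −d × (0, 0.5, 1, 1, 1, 0.5, 0), with d the peak drop in SD units. Month 24 therefore equals the initial visit.

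**Analytic approximation.** Let λ = n d² Σ(c − c̄)², with c the profile weights.
- Σ(c − c̄)² = 3.5 − 4²/7 = 1.214.
- When visits are treated as independent groups, the between-visit mean square behaves as (1 − ρ) χ²₆(λ/(1 − ρ))/6 in units of the variance, and the within-group mean square is close to 1.
- The test therefore rejects when χ²₆ with noncentrality λ/(1 − ρ) exceeds 6 F_crit/(1 − ρ).
- For n = 200, F_crit on 6 and 7 × 199 = 1393 degrees of freedom is 2.105.

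With ρ = 0.8 the threshold is 6 × 2.105/0.2 = 63.2.
- d = 0.3: λ = 200 × 0.09 × 1.214 = 21.86; noncentrality 21.86/0.2 = 109.3; P(reject) ≈ 0.997.
- d = 0.2: λ = 9.71; noncentrality 48.6; P(reject) ≈ 0.26.
- d = 0.1: λ = 2.43; noncentrality 12.1; P(reject) ≈ 0.

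Simulation with 1,000 runs per setting at ρ = 0.8 gave 99.6%, 28.1% and 0.0%, in agreement.

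**Simulation over ρ = 0.5 to 0.9, one-way ANOVA over 7 visits.**

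| Complete patients | Peak drop, fully regained | Overall test significant |
|---|---|---|
| 200 | 0.1 SD | about 0-2% |
| 200 | 0.2 SD | about 18-46% |
| 200 | 0.3 SD | about 97-100% |
| 100 | 0.3 SD | about 31-57% |

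The paired contrast of month 24 with the initial visit has a true mean of zero here, so it rejects at its nominal level, about 5%. At 200 patients and 0.3 SD, 92-95% of runs had a significant ANOVA and a non-significant month-24 contrast.

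**Sensitivity.** With the profile 0, 0.5, 1, 1, 0.8, 0.4, 0, n = 200 and ρ from 0 to 0.9, a 0.3 SD drop gave 93-99% for ANOVA, 92-99% for Kruskal-Wallis and 92-100% for an ANOVA over four time points. At n = 100 the seven-visit ANOVA gave 20-63% at 0.3 SD and 99-100% at 0.5 SD. If values rebounded to 0.2 SD above baseline after a 0.3 SD drop (n = 200), the ANOVA rejected in 100% of runs: the test is blind to direction.

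**The case against.** The strongest objection is that section 10.2 speaks of groups and never says that visits are the groups. The list of tests may be generic, with ANOVA meant for comparisons across comorbidities, BMI strata or degrees of weight loss. The anthropometric comparison can be read as separate two-time-point tests against the initial visit. SF-12 is already framed as initial visit to the end of each stage, the last of which is maintenance, and costs can be a two-period comparison. This stands as far as it goes: under two-time-point tests the problem does not arise. But section 10.2 describes no subgroup comparison, and the two-visit reading still leaves month 24 undesignated for weight, waist, laboratory values and drug use.

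A second objection is that the plan never says an overall p-value proves lasting benefit, and section 10.1 promises means with 95% confidence intervals. Those would reveal a regain if tabulated by visit. Section 10.1 does not say they will be, and intervals for visit means are not intervals for within-patient change.

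Two stronger readings are tempting and fail. A reader might infer that the plan prescribes an overall test across visits and that any regained drop will be significant. The first is only one reading of the text, and the second depends on the size of the drop. A reader might also take the 97-100% as a false-positive rate about 20 times the nominal 5%. It is not: the visit means do differ in these scenarios, so the test correctly rejects its own null. With no change at any visit and correlation of 0.5 or more, it rejects in about 0% of runs, because ignoring the pairing makes it conservative. The fault is that the test answers a different question.

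**Conclusion.** The concern holds conditionally. If the rule for three or more groups is used across visits, a significant result is no evidence that benefit persists at 2 years: with 200 complete patients, a fully regained drop of about 0.3 SD or more would nearly always be significant. For smaller drops or fewer completers the risk is moderate or slight. Whichever reading is taken, the plan does not designate the comparison that answers the long-term objective for weight, waist, laboratory values and drug use.

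The percentages rest on an assumed profile with exact full regain, normal data, equal correlation and no dropout. The documents give no SD or expected change that would place any endpoint on this scale. The figures suit weight, waist and laboratory values best; they do not cover costs and absenteeism, which are likely to be skewed. The change should be made, because a better method is available at almost no cost, but the text does not show that the planned analysis must mislead.

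**What to change.** In section 10.2, replace ANOVA or Kruskal-Wallis across visits with pre-specified within-patient contrasts, each reported as an estimate with a 95% confidence interval:

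- initial visit to month 24, for every long-term claim;
- initial visit to one named short-term visit, for short-term claims. Under section 6, stage 2 ends at 2 + 4 = 6 months or 3 + 6 = 9 months depending on starting BMI, so the visit should be named by stage or by month.

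Paired tests would do, or one mixed model for repeated measures with visit as a category. State that any overall visit test is descriptive. If the three-or-more-group tests are meant for something other than visits, say which groups.

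The cost is a few sentences and contrast statements; the visits and data are already planned. The downside for the sponsor is that a significant overall visit effect can no longer be reported as evidence of long-term benefit, so the result may look less favourable.

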9. ENDPOINTS

9.1. Primary endpoints

The primary variables to be recorded for the study objectives are:

- Consumption of health resources: visits, laboratory controls, admissions ...
- Changes in pharmacological treatment
- Work absenteeism

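### Three unranked primary variables, no primary time frame and a 0.05 level for every test mean that the 5% level does not hold for the primary objective as a whole

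*Combined protocol and SAP*

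**What the plan says.** All references are to the combined protocol and SAP.

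- **Section 9.1** introduces its list with "The primary variables to be recorded for the study objectives are" and gives three items: use of health resources, changes in drug treatment, and work absenteeism. It does not order them or say how many must show an effect.
- **Section 7.2** has a baseline visit "followed by 6 control visits": two in the ketogenic stage, two in the adaptation stage and two in maintenance. Dietitians see patients on a separate schedule and also record medication changes, admissions and absenteeism.
- **Section 10.2** takes expenditure and absenteeism "corresponding to the 6 months prior to the initiation of the weight loss treatment" and says that they "will be compared with data recorded at follow-up visits over the 2-year follow-up". Doses and number of drugs before weight loss and "at the control visits during weight loss and up to completing the 2 years of follow-up will be compared". Neither sentence singles out a visit or a cumulative period.
- **Section 10.2** names the tests for quantitative variables: "using the Student's t-test (in the case of 2 groups) or by the one-way ANOVA test (for 3 or more groups"), with rank-based alternatives for independent groups.
- **Section 10.2** closes with "For all tests, the significance level will be set at" 0.05.

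No section supplies a testing order, a multiplicity adjustment or a rule for when the primary objective is met.

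**The concern.** Section 10.2 says that the comparisons are meant to show whether the treatment improves health and reduces expenditure and absenteeism, and it attaches a fixed significance threshold to them. With three candidate variables and no designated time frame, the plan does not fix which result answers the primary objective. A significant result on any one variable, in any period, could be presented as the answer, and a reader could not tell a planned comparison from a selected one.

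The 5% level then describes each test and not the conclusion that the study will draw. This matters because the primary objective is an economic claim for a named commercial method, and one significant component could carry that claim.

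**Working it through.** The plan states no overall error rate, so there is no figure to reproduce. The check derives one.

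**Inputs from the documents**
- Per-test level: 0.05 (10.2). Sidedness is not stated; two-sided is assumed.
- Primary variables: 3 (9.1).
- Control visits after baseline: 6 (7.2).

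**Inputs assumed**
- Correlations between test statistics. The documents give none, so a range is shown.
- Each test truly has a 5% error rate, which requires paired (within-patient) tests. This is relaxed in step 4.

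**1. One test per variable.** For m independent tests the chance of at least one false positive is 1 − 0.95^m.
- m = 3: 1 − 0.95³ = 14.3%.
- Simulated, correlation 0.3 between variables: 13.6%.
- Simulated, correlation 0.5 between variables: 12.5%.

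A single omnibus test per variable across all visits also gives m = 3.

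**2. Favourable direction only.** Each two-sided test has a 2.5% chance of a false result in the favourable direction.
- Three independent tests: 1 − 0.975³ = 7.3%.
- Correlation 0.3 to 0.5: about 6–7%.

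The benchmark for these figures is 2.5%, not 5%.

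**3. Three variables at six visits each (18 tests).** If all were independent, 1 − 0.95¹⁸ = 60.3%. Repeated visits share patients and a baseline, so independence is not realistic. Simulating 18 correlated normal statistics against ±1.96 gives:

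| Between-visit correlation | Between-variable correlation | Any false positive | Favourable only |
|---|---|---|---|
| 0.5 | 0.3 | about 48% | about 25% |
| 0.7 | 0.3 | about 40% | about 21% |
| 0.8 | 0.5 | about 32% | about 16% |

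**4. The named tests taken literally.** Section 10.2 names tests for independent groups, but the data are within-patient. With equal variances and within-patient correlation ρ, an unpaired test has a true level of 2 × [1 − Φ(1.96/√(1 − ρ))].
- ρ = 0.3: 1.9% per test.
- ρ = 0.5: 0.56% per test.
- ρ = 0.7: 0.03% per test.

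With between-variable correlation 0.3, the 18-test rate falls to about 23%, 8% and 0.6% respectively. Paired tests on the same simulated data return it to about 48%.

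**5. After the fix.** Three tests, each at 0.05/3 = 0.0167, give 1 − (1 − 0.0167)³ = 4.9% if independent. Holm starts from the same 0.0167 and keeps the overall rate at or below 5% whatever the correlation.

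**The case against.** The strongest reply has four parts.

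**The 18-test grid is not in the plan.** This stands. Section 10.2 never says that each visit is tested separately. Expenditure is defined there as a sum of costs, which fits one aggregate comparison, and the ANOVA option fits one omnibus test per variable. Absenteeism and admissions are listed under the dietitians' visits, which follow a different schedule from the six control visits. The grid could also be larger than 18, because doses and number of drugs are both compared. A reader might infer from the six visits that the error rate is 60%, or far above 5% on any reading. The documents do not support that: 60% needs independence, and with one test per variable the rate is about 12–14%.

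**Only a favourable result would be claimed.** This also stands, and it roughly halves the rates. A reader might infer that a positive conclusion is likely by chance. Even on the 18-test reading the favourable-only rate is about 16–25%, so it is not.

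**The unpaired tests are conservative on paired data.** This is arithmetically correct, and with strong within-patient correlation the rate can fall below 5%. But that is an accident of a mismatched test, not planned control. Correcting the test restores the inflation.

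**This is a single-arm observational study that mainly describes.** This stands in part. Section 10.1 plans descriptive statistics with confidence intervals, and no success rule is written, so it is an inference that one significant result would be presented as meeting the objective. How strictly an observational cost study needs overall error control is partly a matter of judgement. But 10.2 also sets a fixed significance threshold for comparisons meant to evaluate a benefit, so it should say which comparisons carry that evaluation.

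**Conclusion.** The concern holds in a bounded form. The plan leaves the primary comparison undesignated in both variable and time, and the 0.05 level does not extend to the primary objective as a whole.

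The base figure is about 12–14% two-sided with one valid test per variable, for between-variable correlations from 0 to 0.5. The higher range of about 32–48% is conditional on separate paired tests at all six visits and on the assumed correlations; the plan permits that reading but does not state it. All of these figures describe valid within-patient tests, not the independent-group tests as written.

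**What to change.** In section 10.2, designate one within-patient comparison for each primary variable:

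1. **Health resource use or expenditure:** rate per patient-month, the 6 months before treatment versus the full 24 months. State which of the two quantities represents this variable.
2. **Work absenteeism:** rate per patient-month, over the same two periods.
3. **Drug treatment:** number of drugs before treatment versus the 24-month visit. A rate per month does not suit this variable, because 10.2 compares it as a state at each time.

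Section 10.2 currently counts drug cost within healthcare expenditure. State whether it stays there or is reported separately, so that the three hypotheses are distinct.

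Test the three with the Holm procedure at an overall 0.05: the smallest p-value against 0.0167, the next against 0.025, the last against 0.05. Replace the independent-group tests with paired methods for these comparisons. Report intermediate visits, cost components and secondary outcomes as estimates with 95% confidence intervals, labelled descriptive.

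The cost is analysis wording only, with no new patients, visits or data. The price is that the smallest of the three p-values must be below 0.0167 before any primary claim is made, and intermediate visits can no longer support one.
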